## Clinical Investigational Plan

Note: If a subject misses one or more of the scheduled follow up visits (inclusive of the assigned visit windows), this will be considered as a missed visit. The subject may therefore still return for subsequent visits and will not be excluded from the study.

If a subject withdraws from the clinical study, the site will record the subject's reasons for withdrawal, on a Withdrawal CRF.

When subject withdrawal from the clinical study is due to an adverse event the subject will be followed until resolution of that adverse event or determination that the subject's condition is stable. The status of the subject's condition should be documented at the time of withdrawal.

### 6.0 Statistical Considerations

The following section describes the statistical methods for the clinical investigation and justification of the design.

#### 6.1 General Statistical Methods

Baseline and procedural data will be presented using appropriate descriptive statistics. Continuous data will be summarized using descriptive statistics including mean, standard deviation, median and range. Categorical data will be summarized by the frequencies and percentages in the corresponding categories.

#### 6.2 Endpoints

##### 6.2.1 Primary Endpoint

The primary safety endpoint is major vascular complications through 30 days, as defined by the Valve Academic Research Consortiumiii (VARC-2) for each access arm of the study.

##### 6.2.1.1 Analysis Methodology

The proportion of subjects experiencing a primary safety endpoint through 30 days (less than or equal to 30 days) post implant will be estimated as the number of subjects who experience the safety endpoint divided by the total number of subjects in the analysis population (see Section 6.2.1.2). The 95% upper confidence limit for the proportion of subjects experiencing a primary safety endpoint will be calculated using the exact binomial method.

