**Clinical Investigational Plan**

Design:	
This is a multicenter prospective, non-randomized, 2-arm investigational study without concurrent or matched controls, designed to assess the use of the Portico TF or Alternative Access Delivery System to place a transcatheter aortic valve through an alternative access site, specifically subclavian/axillary and TAO.
 
A minimum of 45 subjects will undergo transcatheter aortic valve replacement (independent of valve size) using the Portico TF or Alternative Access Delivery System in each study access arm (subclavian/axillary and TAO). A minimum of 45 implants will be accessed via the subclavian/axillary access site and a minimum of 45 implants will be accessed via the TAO access site. A maximum of 12 investigational sites with prior alternative access technique experience in Europe will be trained to participate in the study. Enrollment is anticipated to be completed approximately 8 months from the date of first enrollment. Data will be collected at pre-procedure, peri-procedure and at discharge as well as at 30 days, 6 months and 1 year post implantation. All active subjects will be followed for 1 year.
 
Data from other prospective Portico clinical trials with ALT access in similar patient populations outside of Europe may be included in the analysis and support the submission for CE Mark. CE Mark will be submitted for each access route after implantation and 30 day follow up are completed.
 
Although the study will not test a hypothesis, the primary endpoint event rate for each cohort will be presented within the context of the range of rates reported for alternative access delivery of transcatheter valves in the literature.

Devices used:	
The devices to be used in this study are the Portico delivery systems which are available in two different lengths, 110 and 65cm. Both of these devices are considered investigational for alternative access use. The 110cm delivery system is already CE marked for Transfemoral access. This study will also use the CE marked Transfemoral/Alternative Access Loading systems (18 or 19F) and Portico valves available in 23, 25, 27 and 29mm sizes.

Study Population	
A patient becomes a subject once he/she has been fully informed about the study, has agreed to participate, signed & dated the consent.

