**5.8.2 30-Day Visit**

The 30-Day visit window is 30-7/+14 days after the index procedure, and will include:

1. Physical assessment
2. Barthel Index
3. Modified Rankin Stroke Scale
4. NIH Stroke Scale

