##### 6.2.1.2 Analysis Population

All subjects who have received a Patient Information Sheet, and signed an Informed Consent Form and Data Protection Form will be considered enrolled in the study. However, the analysis population will be based on subjects who have provided signed Informed Consent Form and Data Protection Form and had the SJM TAVI delivery system enter his/her body. The anticipated dropout rate for this study population is expected to be low, as part of the selection criteria is subject compliance with all follow-up visits. Subjects that withdraw from the investigation or are lost to follow-up will not be replaced in the analysis dataset.

It is anticipated that there may be subjects who are enrolled in the study but are not included in the analysis population. There may be subjects who gave consent to participate in the study but did not satisfy the baseline inclusion exclusion criteria, these are considered screen failures. There may also be subjects who have enrolled in the study and started the procedure, but do not have the SJM TAVI delivery system enter his/her body and are procedural exclusions due to their anatomy, circumstances related to the procedure, or physician judgment; these are considered to be procedural exclusion subjects. Screen failure subjects and procedurally excluded subjects will not be part of the analysis population.

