### 6.5 Timing of Analysis

CE Mark will be submitted for each access route. The analyses for CE Mark report will be conducted separately for each access route on datasets locked after 45 subjects in each access route have had the 30-day study visit (excepting deaths, withdrawals and loss-to-follow-up before 30 days) or crossed the 30-day visit window without a visit (missed visit).

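### The 30-day primary rate counts a treated subject with no recorded event and unknown day-30 status as complication-free, so the rate and its upper limit can only err low

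*Combined protocol and SAP*

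**What the plan says.** - **Estimator (6.2.1.1).** The rate concerns subjects "experiencing a primary safety endpoint through 30 days (less than or equal to 30 days) post implant" and is "estimated as the number of subjects who experience the safety endpoint divided by the total number of subjects in the analysis population". On precision: "The 95% upper confidence limit for the proportion of subjects experiencing a primary safety endpoint will be calculated using the exact binomial method".
- **Population (6.2.1.2).** It consists of consented subjects who "had the SJM TAVI delivery system enter his/her body". On incomplete follow-up the section says only: "Subjects that withdraw from the investigation or are lost to follow-up will not be replaced in the analysis dataset". Dropout is expected to be low, but no figure is given.
- **Lock (6.5).** Each route's CE Mark dataset locks once 45 subjects have had the 30-day visit or have "crossed the 30-day visit window without a visit (missed visit"). Subjects who die, withdraw or are lost before day 30 do not hold up the lock.
- **Visit window (5.8.2).** "The 30-Day visit window is 30-7/+14 days after the index procedure", that is, day 23 to day 44.
- **Size (Synopsis, Design).** "A minimum of 45 subjects will undergo transcatheter aortic valve replacement" in each arm, so 45 is a floor.
- **Contrast (6.2.2).** One-year all-cause mortality, cardiovascular mortality and disabling stroke are estimated by Kaplan-Meier with censoring. The 30-day primary endpoint is not.

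**The concern.** The endpoint is defined to day 30, but neither the estimator nor the lock rule asks whether a subject was observed to day 30. Section 6 gives no rule for unknown status. The formula then settles the matter by default: no recorded event means no event.

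This is a safety rate in a study without a control group, and its upper limit is the precision statement. Unobserved events can only pull both figures down. The exact interval also treats all 45 outcomes as known, so it does not show the missing information. In arms of 45 each subject is worth 2.2 percentage points (1/45), so a few unknowns can matter to how the result reads against the literature range of 5% to 23.3% in section 6.6.

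**Working it through.** **Inputs.** From the documents: n = 45 per route, assumed rate 5.9%, exact 90% interval 1.45% to 15.32% (6.3); one-sided 95% exact upper limit (6.2.1.1); literature range 5% to 23.3% and pooled rate 11.9% (6.3, 6.6). Assumed, because the documents give no figure: the number of observed events x, the number m with unknown day-30 status, the fraction d with incomplete follow-up, and the share s of events that occur before that follow-up ends.

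**Step 1: reproduce the plan's interval.** The exact upper limit is U(x, n) = 0.95 quantile of Beta(x+1, n−x). The lower limit is the 0.05 quantile of Beta(x, n−x+1). With x = 45 × 0.059 = 2.655, these give 1.45% and 15.32%, matching section 6.3. The upper end of that 90% interval is the 95% upper limit of 6.2.1.1.

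**Step 2: who is counted as what.**
- Event recorded by day 30: in the numerator, even if the subject later withdraws or is lost.
- Death by day 30 without the event: status known, correctly a zero.
- Withdrawn or lost before day 30 with no recorded event: status unknown, counted as a zero.
- Missed visit, or visit on days 23–29, with no recorded event: counted as a zero without a required check to day 30. A day-23 visit leaves 30 − 23 = 7 endpoint days not covered by that visit.

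**Step 3: effect on the upper limit.** With 3 observed events, the plan as written gives 3/45 = 6.67%, upper limit 16.34%, whatever m is.

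| m unknown | Unknown removed: rate, upper limit | All unknown counted as events: rate, upper limit |
|---|---|---|
| 1 | 3/44 = 6.82%, 16.69% | 4/45 = 8.89%, 19.20% |
| 2 | 3/43 = 6.98%, 17.06% | 5/45 = 11.11%, 21.95% |
| 3 | 3/42 = 7.14%, 17.44% | 6/45 = 13.33%, 24.63% |
| 5 | 3/40 = 7.50%, 18.26% | 8/45 = 17.78%, 29.80% |

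For 1 to 3 unknown, removal raises the limit by 0.35 to 1.10 points (16.69 − 16.34; 17.44 − 16.34). The worst case raises it by 2.86 to 8.29 points (19.20 − 16.34; 24.63 − 16.34).

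With other event counts and m = 3, the limits as written, removed and worst case are 13.34%, 14.24% and 21.95% for 2 events, and 21.95%, 23.42% and 29.80% for 5 events.

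**Step 4: expected bias.** If incomplete follow-up is unrelated to event risk, the rate is understated on average by p × d × (1 − s).
- p = 5.9%, d = 5%: 0.30 points at s = 0, 0.06 at s = 0.8.
- p = 5.9%, d = 10%: 0.59 points at s = 0, 0.12 at s = 0.8.
- p = 11.9%, d = 10%: 1.19 points at s = 0, 0.24 at s = 0.8.

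**The case against.** The strongest reply is that event capture does not depend on the 30-day visit. Safety surveillance runs from consent to the last visit, death or withdrawal, and vascular complications are reportable within 72 hours of first learning of them (9.2). Subjects who miss a visit stay in the study, and those who cannot be located are traced through the general practitioner (5.15), which the monitor verifies (11.0). Subjects with delivery-system entry but no valve are followed for 30 days for adverse events (5.7.4). With about 8 months of enrolment, nearly everyone is well past day 30 at lock. Follow-up continues to 1 year, so a late-reported event can still enter later reporting.

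Much of this stands, and it rules out four stronger readings that a reader might infer:

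- **That all withdrawn, lost, missed-visit and day-23 subjects count as complication-free.** They do not. A recorded event by day 30 counts in every case, and missed-visit and day-23 subjects remain under safety reporting. For those two groups the gap lies mainly at the CE Mark lock.
- **That subjects treated just before lock dilute the denominator.** Although 45 is a minimum, 6.5 does not say that later-treated subjects enter the locked dataset. The text is open on this.
- **That a worst-case limit of 24.6% means the study could miss its criterion.** That figure needs 3 of 45 unknown and all 3 with events. Section 6.6 has no formal hypothesis and sets the result against the range; the worst-case rate of 13.3% lies inside it. The remark on the upper limit in 6.3 is a sample-size rationale and not a decision rule.
- **That the denominator should be restricted to subjects with confirmed status.** A subject lost on day 20 would then be kept if an event had occurred and dropped if not, which can bias the rate upward.

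What the reply does not answer is that none of these provisions requires status through day 30 to be documented before lock. Nor do they generally recover events after withdrawal, when surveillance normally ends.

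**Conclusion.** The point holds in a limited form. The plan states a full-denominator rule, allows lock with incomplete 30-day information, and has no status check. Any subject with no recorded event and unknown day-30 status is scored as event-free, and the error from this source runs in one direction only.

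The size is likely small. At a true rate of 5.9% with 5% to 10% incomplete, the expected understatement is 0.06 to 0.59 points over the assumed values of s (0 to 0.8). It would be larger if subjects with complications were more likely to be lost. That access-related events cluster early is plausible but is not stated in the documents. The worst-case limits are bounds and not forecasts. The case for acting rests on the known direction of the error, the small arms, the unquantified dropout and the low cost of the remedy.

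**What to change.** Keep the full treated denominator as the primary analysis.

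**Section 6.5.** Before lock, require documented major-vascular-complication status through day 30 for every subject seen on days 23–29 or with a missed visit. A contact on or after day 30, or death by day 30, would satisfy this. Define the locked cohort by procedure date, without regard to outcome, so that every member has reached day 30. Excluding recently treated subjects in any other way could discard complications already observed. Complications already recorded in subjects treated after the cut-off can be listed separately.

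**Section 6.2.1.1.** Report the number with unconfirmed day-30 status. Add two sensitivity rows:
1. A Kaplan-Meier 30-day estimate that censors incomplete follow-up. Deaths by day 30 without the event should be carried as event-free to day 30, so that the estimate equals the primary proportion when follow-up is complete.
2. An exact 95% upper limit counting every unconfirmed subject as an event, labelled as a bound.

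**Cost.** Plan wording, a few contacts before lock and two table rows. The downside is a slightly less favourable figure shown beside the primary result.

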##### 6.2.1.2 Analysis Population

All subjects who have received a Patient Information Sheet, and signed an Informed Consent Form and Data Protection Form will be considered enrolled in the study. However, the analysis population will be based on subjects who have provided signed Informed Consent Form and Data Protection Form and had the SJM TAVI delivery system enter his/her body. The anticipated dropout rate for this study population is expected to be low, as part of the selection criteria is subject compliance with all follow-up visits. Subjects that withdraw from the investigation or are lost to follow-up will not be replaced in the analysis dataset.

It is anticipated that there may be subjects who are enrolled in the study but are not included in the analysis population. There may be subjects who gave consent to participate in the study but did not satisfy the baseline inclusion exclusion criteria, these are considered screen failures. There may also be subjects who have enrolled in the study and started the procedure, but do not have the SJM TAVI delivery system enter his/her body and are procedural exclusions due to their anatomy, circumstances related to the procedure, or physician judgment; these are considered to be procedural exclusion subjects. Screen failure subjects and procedurally excluded subjects will not be part of the analysis population.

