**5.7.4 Procedural Exclusion**

During the procedure, the implanting investigator may determine transcatheter aortic valve implantation using the Portico TF or ALT Delivery System is neither feasible nor in the best interest of the subject. Any subject that does not have a delivery system enter his or her body will be withdrawn from the study. Data collected on these subjects, at baseline, will consist of reason(s) for exclusion and possible adverse events. Subjects that have a Delivery System enter his or her body but no valve will be followed for 30 days to collect adverse events.

Following the procedure, the delivery and loading systems should be securely disposed of per hospital requirements for hazardous materials. If there are any concerns noted with the delivery system, loading system, or valve during the procedure, they should be reported and returned to Abbott.

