### 6.3 Sample Size

The sample size of 45 subjects for each access route is based on the desire to estimate the rate of 30-day vascular complication with a sufficient degree of precision. The rate of major vascular complications at 30 days in Portico TF EU study was 5.9%. The rate of major vascular complications reported for other TAVI valves at 30 days in a weighted meta-analysis of 3,519 patients from 16 studies ranged from 5.0% to 23.3%. The same meta-analysis calculated a major vascular complication pooled estimate 30-day rate of 11.9% (95% CI 8.6%-16.4%). Assuming an event rate of 5.9%, with 45 subjects, the exact 90% CI is (1.45%, 15.32%). Therefore, a sample size of 45 will result in the 90% confidence interval half-width of 9.42% and the 95% upper confidence limit is within the range reported in the literature

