### 6.4 Justification of Clinical Investigation Design

The Portico valve has demonstrated safety and favorable clinical results via TF access in the TF EU Portico Trial (n=222). The study will evaluate the safety of alternative access for the approved Portico transcatheter aortic and includes a primary safety endpoint of major vascular complications at 30 days. This endpoint is appropriate because vascular access is the only new aspect being investigated in this study and 30-days has been established by VARC2 as the appropriate time period to assess early safety events such as major vascular complications.

Numerous studies have demonstrated that vascular complication rates at 30 days with ALT access are similar to that of the TF approach and that survival at 1 and 2 years is similar between the subclavian and the TF approach. The sample size of 45 subjects is adequate to ensure that the rate of the primary endpoint, major vascular complications at 30 days, is consistent with the rate for Portico valves delivered by TF access as well as with rates reported in the literature.

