### Acute Device Success (VARC)

Acute device success is defined as a subject who achieves a) successful vascular access, delivery and deployment of the device and successful retrieval of the delivery system, b) correct position of the device in the proper anatomical location, c) intended performance of the prosthetic heart valve, and d) only 1 valve implanted in the proper anatomical location.

Device success is a 'technical' composite endpoint meant to characterize the acute device and procedural factors which underlie vascular access, delivery, and performance of the TAVI system. Echocardiography should be routinely utilized as the standard for measuring prosthetic valve stenosis and regurgitation immediately after TAVI, and should always be performed in a resting state, either within 24–48 h after the index procedure or before hospital discharge.

Prosthetic Valve Stenosis Criteria In conditions of normal or near normal stroke volume (50–70 ml). (VARC2)	Parameter	Normal	Mild Stenosis	Moderate/severe Stenosis
	Peak velocity (m/s)	less than 3	3–4	greater than 4
	Mean gradient (mm Hg)	less than 20	20–40	greater than 40
	Doppler velocity index	greater than or equal to 0.35	0.35–0.25	less than 0.25
	Effective orifice area (cm  )	greater than 1.1*	1.1–0.8	less than 0.80
Prosthetic Valve Regurgitation Criteria (Central and Paravalvular)	Parameter	Mild	Moderate	Severe
	Valve structure and motion	Usually normal	Usually abnormal	Usually abnormal
	Left ventricular size	Normal	Normal/mildly dilated	Dilated
	Doppler parameters ( qualitative or semiquantitative )			

\* Effective orifice area (EOA) used in this protocol is 1.0 cm^2 for Portico valve of 23 mm diameter.

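### The primary analysis population leaves out procedures stopped before the delivery system enters, so an access injury that stops the case can fall outside the access-safety rate, which may then be understated

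*Combined protocol and SAP*

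**What the plan says.** Section 6.2.1.1 defines the primary rate as subjects with the endpoint "divided by the total number of subjects in the analysis population". Section 6.2.1.2 admits to that population only consented subjects whose delivery system entered the body. It describes a group who started the procedure without entry, for reasons of anatomy, procedural circumstances or physician judgment, and calls them procedural exclusions. It then states: "Screen failure subjects and procedurally excluded subjects will not be part of the analysis population". No exception is made where the reason was an access injury, and no sensitivity analysis that includes these subjects is described.

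Section 5.7.4 adds: "Any subject that does not have a delivery system enter his or her body will be withdrawn from the study". For these subjects it keeps the reason for exclusion and possible adverse events. Subjects with entry but no valve are followed for adverse events for 30 days.

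The endpoint definition in Appendix D covers serious access-site or access-related vascular injury, and any aortic dissection or rupture. It does not require that a delivery system entered. Section 6.4 justifies the endpoint on the ground that "vascular access is the only new aspect being investigated in this study".

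**The concern.** Both routes require access to be gained before the delivery system goes in. Section 2.0 describes the transaortic approach as a ministernotomy or mini-thoracotomy with direct aortic cannulation. A dissection, perforation or rupture at that stage can be a qualifying event and can also be why the operator stops. That subject then leaves both the numerator and the denominator. Whether a subject is analysed can therefore depend on whether the subject had the event.

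At stake is the credibility of the single primary endpoint. Each arm has about 45 subjects and no concurrent control, and its rate is read against published rates. One event moves the estimate visibly, and no comparison arm would be affected in the same way.

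**Working it through.** **Inputs.** Planned size is 45 per route and the assumed rate is 5.9% (Section 6.3). The limit is the exact binomial 95% upper limit (Section 6.2.1.1), which equals the upper end of a two-sided 90% interval. The expected range is 5% to 23.3% (Section 6.6). The number of procedural exclusions and their injury rate are not given, so the scenarios below are assumptions.

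**Formula.** For x events in n subjects, the exact limits are

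- lower = 5th percentile of Beta(x, n − x + 1)
- upper = 95th percentile of Beta(x + 1, n − x)

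**The plan's own figure.** With n = 45 and x = 45 × 0.059 = 2.655, the limits are 1.45% and 15.32%. This matches Section 6.3.

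**Scenarios.** The base case is 3 events in 45, the whole number nearest to 2.655. Adding m procedural exclusions, of whom e had a qualifying injury, gives a rate of (3 + e)/(45 + m).

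| Added (m) | Injured (e) | Rate | 95% upper limit |
|---|---|---|---|
| 0 | 0 | 3/45 = 6.67% | 16.34% |
| 1 | 1 | 4/46 = 8.70% | 18.80% |
| 2 | 2 | 5/47 = 10.64% | 21.08% |
| 3 | 3 | 6/48 = 12.50% | 23.19% |
| 3 | 1 | 4/48 = 8.33% | 18.06% |
| 5 | 0 | 3/50 = 6.00% | 14.78% |

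Each injured exclusion adds about 2 points to the rate and 2 to 2.5 points to the limit. Two of them raise the rate by about 60% in relative terms (10.64/6.67 = 1.60).

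**Direction.** (3 + e)/(45 + m) exceeds 3/45 only when e/m exceeds 3/45, that is, when more than 1 in 15 of the added subjects was injured. The exclusion understates the rate only if the excluded subjects have a higher injury rate than the analysed ones.

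**The case against.** The best defence is that the devices under investigation are the delivery systems (Section 3.1), so a population defined by device exposure is coherent, disclosed and prespecified. That is fair, and it is a reason to keep the entry-based set in the report. It does not answer Section 6.4, which rests the choice of endpoint on access.

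Several stronger readings are tempting, and the documents do not support them.

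- *The primary rate is biased downward.* This is conditional. Some procedural exclusions will be uninjured, and including them would lower the rate. Section 6.2.1.2 also speaks of starting the procedure, without defining that as incision or puncture, so some of these subjects may never have had access attempted.
- *These injuries go unseen.* Section 5.7.4 collects possible adverse events, and Section 9.2 makes vascular complications and all serious adverse events reportable. Section 5.15 follows a subject withdrawn because of an adverse event until it resolves or the condition is stable, which may well cover a subject stopped by an access injury. What is missing is their place in the primary rate and an assured 30-day assessment.
- *Every aborted case is lost.* An injury that stops the case after entry is counted, even with no valve implanted.
- *A subject converted between routes counts only where access succeeded.* The plan has no rule on conversion, so nothing can be concluded either way.
- *Access success is inflated.* Appendix D does include "successful vascular access, delivery and deployment of the device and successful retrieval of the delivery system" in acute device success. But Section 6.2.2 points to the definition in Section 4.3.2, which omits access as a component and says only that access success will be collected. No access-success rate or denominator is specified.

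**Conclusion.** The concern holds in a limited form. Followed as written, Sections 6.2.1.2 and 5.7.4 can remove a primary-endpoint event because of the event itself, so the major vascular complication rate may be understated in either arm.

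The size cannot be derived from the documents. One or two excluded injuries per arm is an assumption; it would move 6.7% to 8.7% or 10.6%, and the upper limit from 16.3% to 18.8% or 21.1%. A reader might infer that the conclusion would be overturned. It would not in these scenarios: the estimates and upper limits stay inside the 5% to 23.3% range in Section 6.6, and even three excluded injuries give a limit of 23.19%. There is also no formal hypothesis to fail.

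No stated figure is wrong on this account. The point should be fixed because the remedy is cheap and because 30-day data not collected at the time cannot be reliably recovered later.

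**What to change.** In Section 6.2.1.2, analyse the primary endpoint in all subjects in whom access was attempted (skin incision or arterial puncture), assigned to the first attempted route. Report the delivery-system-entered set alongside it. Subjects who fail screening before any access attempt stay out.

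In Section 6.2.1.1, count the 30 days from the index procedure. The present count starts at implant, which gives no starting point for a subject without one; Section 6.2.2 already uses the index procedure as Day 0 for the one-year analyses.

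In Section 5.7.4, collect adverse events to 30 days for attempted-access subjects without entry, as is already done for those with entry but no valve.

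If the sponsor prefers to keep the present primary population, the minimum is to prespecify the attempted-access set as a sensitivity analysis and to report procedural exclusions by arm, with reasons and access injuries. The 30-day adverse event collection is needed in either case.

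The cost is a protocol amendment, follow-up of probably a few more subjects, and a reported rate that may be less favourable.
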